#### 2.5.2.2 Male Endpoints

Penile and glans penis swabs, scrotal swabs, and perineal/perianal swabs will be tested for detection of HPV 6, 11, 16, 18, 31, 33, 35, 39, 45, 51, 52, 56, 58, and 59 by PCR assay. PCR analysis of the swabs will be used to determine persistent HPV infection endpoints.

A thorough external genital wart/lesion inspection will be performed at routine visit intervals. External genital warts/lesions will be biopsied.

Tissue obtained from biopsy procedures will be analyzed by MRL HPV Thinsection PCR assay (detection of HPV 6, 11, 16, 18, 31, 33, 35, 39, 45, 51, 52, 56, 58, and 59) and by a consensus diagnosis from the HPV Vaccine Program Pathology Panel to determine clinical disease efficacy endpoints.

### 2.6 LIST OF SAFETY MEASUREMENTS

The following serious adverse experiences will be collected for the duration of the study:

- Death of a study subject
- Serious adverse experiences (as defined in Section 3.4) judged by the study investigator to be related to prior administration of 9-valent HPV L1 VLP vaccine.
- Serious adverse experiences (as defined in Section 3.4) judged by the study investigator to be related to a study procedure.

Pregnancy information and infant serious adverse experiences will also be collected.

# 2.7 STATISTICAL ANALYSIS PLAN SUMMARY

Key elements of the statistical analysis plan are summarized below; the comprehensive plan is provided in Section 3.5.

19

# 2.7.1 Immunogenicity Analyses

Immunogenicity summaries are planned to occur at three time points, to include followup data through Month 72, Month 96, and at the end of the study at Month 126. Geometric mean titers (GMTs) and seropositivity rates for each vaccine HPV type will be summarized by gender, and age group (determined by age at enrollment), along with associated 95% confidence intervals. Longitudinal plots of anti-HPV levels will be provided for each HPV type. The primary analysis will be per-protocol.

In addition, exploratory analyses regarding the kinetics and persistence of the antibody response may be conducted, with particular interest in the effect of age at first vaccination on duration of anti-HPV levels. Modeling techniques may be used to study the relationship between anti-HPV persistence and factors such as time since vaccination, age at vaccination, age at sexual debut, and GMT at 1 month post-dose 3.

# 2.7.2 Effectiveness

At the time of the first interim analysis (Month 72), summaries of the incidence of HPV 6, 11, 16, 18, 31, 33, 45, 52, and 58 related persistent infection for a duration of  $\geq 6$  months (within  $\pm 1$  month windows) and cervical, vulvar, vaginal, perineal, perinal, and penile intraepithelial preinvasive and invasive disease, and external genital lesions will be provided, separately for males and females. Similar summaries of the incidence rates of HPV 6, 11, 16, 18, 31, 33, 45, 52, and 58-related persistent infection for a duration of  $\geq 6$  months (within  $\pm 1$  month windows) and disease will be provided to include follow-up data through the second interim analysis at Month 96 and at the end of the study at Month 126.

All subjects will contribute to the effectiveness summaries. Summaries will be provided by gender and age group (based on age at enrollment). The primary analysis group will be those who have received 3 doses of 9-valent HPV L1 VLP vaccine within one year. Subjects will be considered breakthrough cases related to a given HPV type provided they were negative to the respective HPV type by serology prior to vaccination and were sexually naïve through the 3rd dose of 9-valent HPV L1 VLP vaccine. Sexual naïveté, an inclusion criterion for the base study, is being used as a way to limit analysis of the prophylactic effect of the vaccine to subjects who were not infected prior to completion of the vaccination series. There are no PCR data from Protocol V503-002 subjects until subjects reach their 16th birthday. Therefore, the only data available to assess possible prior infection are pre-vaccination serum anti-HPV levels and sexual history. Cases in subjects with evidence of HPV exposure or infection prior to vaccination (i.e., seropositivity to the relevant HPV type(s) pre-vaccination or sexual activity prior to completion of the vaccination series) or in subjects who did not receive 3 doses of 9valent HPV L1 VLP vaccine within one year will not be considered breakthrough cases (vaccine failures). Such cases will be summarized separately.

20

At each analysis time point, the cumulative (from the start of this extension) incidence rate for effectiveness endpoints will be computed, along with the associated 95% confidence intervals. Time-to-event plots will also be provided by gender if >5 cases are observed. In addition, exploratory analyses will be conducted to characterize subjects who become cases of persistent infection or disease endpoints in the long-term effectiveness follow-up period. Baseline demographic characteristics, pre-vaccination anti-HPV serology status, and post-vaccination immunogenicity profiles will be considered. Incidence rates for the same endpoints caused by HPV types not contained in the vaccine will also be summarized, when such data are available. An additional analysis of persistent infection for a duration of 12 months (within  $\pm$  1 month windows) or more may be conducted.

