#### PRIMARY REASON FOR THIS AMENDMENT:

Protocol V503-002-20 is an extension of Protocol V503-002-10. Protocol V503-002-20 will assess long-term immunogenicity, safety, and effectiveness of 9-valent HPV L1 VLP vaccine, when administered to 9- to 15-year-old girls and boys through active follow-up of study subjects for up to 10 years post-dose three.

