### 2.4 STUDY DESIGN AND DURATION

### 2.4.1 Summary of Study Design

Protocol V503-002-20 is an international, multicenter study designed to evaluate the long-term immunogenicity, safety, and effectiveness of 9-valent HPV L1 VLP vaccine in subjects who were enrolled in Protocol V503-002 when they were between 9 and 15 years of age and received 3 doses of 9-valent HPV L1 VLP vaccine. Under the base study (Protocol V503-002), subjects were administered a 3-dose regimen of 9-valent HPV L1 VLP vaccine and assessed for immunogenicity (at Day 1 and Month 7) and safety (Day 1 through Month 12). Under Study Extension V503-002-10, subjects will complete the Month 36 visit (which is the last visit in Protocol V503-002-10) before starting in Protocol V503-002-20. The long term follow-up period under Protocol V503-002-20 will start at the Month 42 visit and end at the Month 126 visit (approximately 7.5 years later and approximately 10 years post-dose 3).

Visit schedule and study endpoints will vary depending on age and gender.

- Prior to reaching 16 years of age, subjects will have an annual visit. Serum samples will be obtained and safety information will be collected as outlined in Section 2.6
- Starting at age 16 years, visits will be twice a year. In addition to serum samples (collected yearly) and safety information, visits will include the collection of sexual history, genital examination and genital clinical specimens. Genital examination and types of clinical specimens collected will be age and gender specific, and in females, depend in part on sexual activity, as described below:
  - 1. For female subjects 16 to 20 years of age who are not sexually active, each visit will include external genital lesion examination and collection of labial/vulvar/perineal/perianal (LVPP) swabs. Chlamydia/gonorrhea testing will be performed annually based on urine sample.

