#### **3.5.5.3 Statistical Methods for Effectiveness Analyses**

Subjects who meet the criteria to be considered cases of vaccine type HPV-related persistent infection and/or disease, but who have evidence of HPV exposure or infection (i.e., seropositivity to the respective HPV type(s) pre-vaccination or evidence of sexual activity prior to the completion of their vaccination series), or who do not complete their three doses of 9-valent HPV L1 VLP vaccine within one year, will not be considered breakthrough cases (i.e., vaccine failures). Such cases will be summarized separately in a manner similar to breakthrough cases, with all relevant factors such as baseline demographics and immunogenicity profiles over time characterized; however, these cases will not be included in the primary summary of effectiveness endpoints.

78

At the time of the interim analysis (Month 72), summaries of the incidence of HPV 6, 11, 16, 18-related persistent infection for a duration of  $\geq 6$  months (within  $\pm 1$  month windows) and cervical, vulvar, vaginal, perineal, perinanal, and penile intraepithelial preinvasive and invasive disease, and external genital lesions will be provided, separately for males and females. Similar summaries of the incidence rates of HPV 6, 11, 16, 18, 31, 33, 45, 52, and 58-related persistent infection for a duration of  $\geq 6$  months (within  $\pm 1$  month windows) and disease will be provided to include follow-up data through Month 96 and Month 126.

The confidence intervals around the point estimate of the incidence rates per 100 personyears are exact Poisson distribution-based nominal 95% confidence intervals.

Summaries will be provided by gender. At each analysis time point, the cumulative incidence rate for effectiveness endpoints will be computed, along with the associated 95% confidence interval. In addition, exploratory analyses will be conducted to characterize subjects who become cases of persistent infection or disease endpoints in the long-term effectiveness follow-up period. Baseline demographic characteristics, prevaccination anti-HPV serology status, and post-vaccination immunogenicity profiles will be considered. Time-to-event plots will also be provided by gender if >5 cases are observed in the respective group(s).

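### The planned effectiveness rate pools all extension follow-up, so a rise in breakthrough incidence in the years nearest 10 years post-dose 3 is averaged with earlier years; rates by period should be added

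*Combined protocol and SAP*

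**What the plan says.** Section 2.7.2: "At each analysis time point, the cumulative (from the start of this extension) incidence rate for effectiveness endpoints will be computed", with a 95% confidence interval. Section 3.5.5.3 has the same sentence without the bracket: "At each analysis time point, the cumulative incidence rate for effectiveness endpoints will be computed". It adds that rates per 100 person-years carry "exact Poisson distribution-based nominal 95% confidence intervals".

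The first summary is at Month 72. Later ones are to include "follow-up data through the second interim analysis at Month 96 and at the end of the study at Month 126". Each cut contains the one before it.

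The one output that shows timing within follow-up is graphical: "Time-to-event plots will also be provided by gender if >5 cases are observed" (2.7.2). Section 3.5.5.3 applies the same condition to the respective group. Neither section gives the plots a time origin or an interval estimate. The other breakdowns are by gender, by age group at enrolment (2.7.2) and by endpoint component (3.5.3.3), and none is by time.

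On purpose, the reason given for the amendment is to assess long-term immunogenicity, safety and effectiveness "through active follow-up of study subjects for up to 10 years post-dose three". The two co-secondary objectives (2.1.2) are to estimate long-term effectiveness in girls and in boys.

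The antibody analysis is planned differently. Section 3.5.5.1 gives titres and seropositivity rates with intervals at each sampling time, and names time since vaccination as a modelling factor. The effectiveness analysis has no counterpart.

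**The concern.** The extension is run to Month 126 to learn about the later years. A rate accumulated from Month 42 answers how many breakthrough cases occurred per person-year over the whole extension. It does not say what the incidence was between roughly 7.5 and 10 years post-dose 3, which is the part of follow-up that shorter studies cannot supply. If breakthrough incidence rose late, the Month 126 figure would move by less than the true change. If it did not rise, the pooled interval would hide how little information stands behind that statement for the last years.

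**Working it through.** The plan has no figure to reproduce: the sample size is fixed by participation and no hypothesis is tested (2.7.4, 3.5.7). The calculations below are illustrations.

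**1. The clock.** Dose 3 was given at Month 6 (3.2.2.1), so years since dose 3 = (study month − 6)/12. Months 42, 72, 96 and 126 give 3.0, 5.5, 7.5 and 10.0 years.

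**2. Person-time by period.** From the documents: follow-up runs from Month 42 to Month 126, effectiveness data start at age 16 (1.4), and age at enrolment was 9 to 15. Assumed: age is uniform from 9 to just under 16, entry is at the later of Month 42 and the 16th birthday, and there is no dropout. The 16th birthday then falls uniformly over Months 0 to 84. The fraction under observation at Month t is t/84 up to Month 84 and 1 afterwards. Mean person-months per subject:

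- Months 42-72: (72² − 42²)/(2 × 84) = 3420/168 = 20.4
- Months 72-96: (84² − 72²)/168 + 12 = 11.1 + 12 = 23.1
- Months 96-126: 30.0
- Total 73.5; shares 28%, 31%, 41%

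With dropout rising linearly to 30% by Month 126, the fraction is multiplied by 1 − 0.3(t − 42)/84. The shares become 31%, 32% and 37%. With 8% annual loss the last share is 34%.

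**3. Dilution.** If the true rate is multiplied by k after Month 96 and the last share is s, the cumulative rate is multiplied by 1 + s(k − 1).

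| Dropout | s | k = 2 | k = 3 |
|---|---|---|---|
| None | 0.408 | 1.41 | 1.82 |
| 30% linear | 0.368 | 1.37 | 1.74 |
| 8% per year | 0.344 | 1.34 | 1.69 |

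**4. What a period rate would add.** Assume 1200 subjects in one gender (the documents give 2552 eligible in all, without a split), 8% annual loss, an early rate of 0.1 per 100 person-years and a tripling after Month 96. Person-years are 1821, 1727 and 1861, total 5409. Expected cases are 3.55 early and 5.58 late. Rounding the late and total counts to whole cases:

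- Cumulative: 9/5409 = 0.17 per 100 person-years, exact 95% CI 0.08 to 0.32
- Months 96-126: 6/1861 = 0.32, exact 95% CI 0.12 to 0.70

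The chance that the lower limit exceeds the early rate is 31% for the cumulative rate and 49% for the period rate. Over the settings tried with a tripling (600 or 1200 subjects, no loss or 8% annual loss, early rate 0.1 or 0.2), it is 18-73% against 31-95%.

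**5. The plots.** With a tripling and an early rate of 0.1, the chance of 5 or fewer cases in a gender, hence no plot, is 34-69% with 600 subjects and 1-11% with 1200. With an early rate of 0.2 it is at most 11%.

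**6. Subtraction.** Months 96-126 can be recovered if both cases and person-years are tabulated at Month 96 and at Month 126. For Months 72-96, section 3.5.5.3 words the Month 72 summary for HPV 6, 11, 16 and 18, whereas 2.7.2 and 3.5.9 name all nine types. Under the 3.5.5.3 wording that period could not be derived for nine types. The plan provides for neither subtraction.

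**The case against.** The case for leaving the plan alone has real force.

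- **The cumulative rate is not the only output.** A reader might infer that effectiveness is reported solely as one pooled figure. That goes too far. Summaries at Months 72, 96 and 126 are nested, plots are planned, and exploratory work will describe the cases, including their antibody profiles. What stands is that no separate-period rate with its own interval is pre-specified, and that the plots are conditional.
- **Study month does track time since dose 3.** Younger vaccinees enter effectiveness follow-up later, up to Month 84 for a child enrolled at exactly 9, so a reader might infer that study time is a poor stand-in for time since vaccination. It is not: dose 3 is at Month 6 for everyone and later visits are scheduled from there. Late entry changes who contributes to each period, not the clock. It matters mainly for the unstated origin of the plots.
- **A late rise is not waning.** A reader might infer that period rates would reveal a loss of protection. The documents do not support that. All participants were vaccinated (3.5.1), and the protocol's own background says that HPV incidence in women rises through the teens and peaks in the early twenties (3.1.1.3.1). A higher late rate is plausible with constant efficacy. For the same reason, a rule that any 10-year conclusion must rest on the last period alone would be hard to defend.
- **The objective is broad.** The explicit 10-year wording in section 2.1 belongs to the antibody objective (2.1.1). The effectiveness objectives say long-term, and sections 1.3 and 3.1.2.1 make effectiveness conditional on the data. A rate accumulated over follow-up is a legitimate answer to that.
- **The gain is moderate.** The last period holds the largest single share of person-time, and a tripling would still raise the cumulative rate by about 70-80%.

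These points limit what may be claimed. They do not remove the case for a few extra table rows.

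**Conclusion.** The point holds as a cheap improvement, not as an error that threatens the study. The rate estimate planned in 2.7.2 and 3.5.5.3 averages the years nearest 10 years post-dose 3 with earlier follow-up. Under the stated assumptions the last 30 months carry about 41% of person-time (37% with 30% linear dropout), so a doubling after Month 96 would show as about 1.4-fold. These shares rest on an even age distribution, entry at the later of Month 42 and age 16, and the dropout patterns shown; the documents give none of these distributions. The case counts and detection chances rest further on assumed rates and numbers per gender. The absence of a pre-specified period rate rests on no assumption.

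**What to change.** In section 3.5.5.3, and briefly in 2.7.2, add the following at each analysis, by gender and beside the cumulative rate:

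- number of cases, person-years and incidence per 100 person-years with exact Poisson 95% CI for Months 42-72, >72-96 and >96-126 (about 3 to 5.5, 5.5 to 7.5 and 7.5 to 10 years post-dose 3), for any number of cases, as far as follow-up has reached;
- the share of subjects sexually active in each period, from the sexual history already collected (3.2.2.6) and summarised (3.5.5.4);
- the time origin of the time-to-event plots;
- a sentence that differences between periods are descriptive, because exposure rises with age, the mix of subjects changes as younger vaccinees reach 16, and there is no unvaccinated group.

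The cost is plan wording and three rows per table. It needs no new visits, samples or tests, and it uses the plan's own cut-offs and interval method. The downside is precision: with a tripling, the settings above give only about 3 to 18 late cases per gender, so intervals will be wide. A single late figure must not be read as evidence of waning, nor a low one as proof of durability.

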### 2.7.3 Safety analysis

All subjects who received at least one dose of 9-valent HPV L1 VLP vaccine and have long-term study follow-up data will be included in the safety summaries. Listings of serious adverse experiences and deaths, and a pregnancy summary will be provided.

# 2.7.4 Power and sample size

The sample size for this long-term follow-up study is fixed by the number of Protocol 002 participants who are eligible and willing to participate in the extension. There is no formal hypothesis that will be tested in this long-term follow-up study. A total of approximately 2600 subjects, 9 to 15 years of age, were enrolled in the V503-002 base study.

### 2.7.5 Interim Analysis

Interim analyses will be conducted at Month 72 and Month 96 to assess the feasibility of obtaining 10 full years of follow-up. The decision to continue with the effectiveness component of the study will depend on the ability to collect sufficient effectiveness data observed through Months 72 and 96, and anticipated through the remainder of the study. Summaries of the incidence of persistent infection and cervical, vulvar, vaginal, perineal, perianal, and penile intraepithelial preinvasive and invasive disease, and external genital lesions related to HPV 6, 11, 16, 18, 31, 33, 45, 52, and 58 will be provided separately for males and females.

# **3. PROTOCOL DETAILS**

21

#### 3.1 RATIONALE

#### **3.1.1 Introduction to Human Papillomavirus**

HPV infection causes benign and malignant dysplastic disease, localized primarily in the anogenital area and aerodigestive tract, in both men and women [2; 3; 4].

#### 3.1.1.1 Disease Burden

**Cervical Cancer and Precancerous Dysplasia.** Nearly 100% of cervical cancers are caused by HPV infection [5; 6]. Cervical cancer is the second most common cancer in women worldwide [7], with approximately 530,000 new cases diagnosed each year and 275,000 annual deaths [8; 9]. Most (~80%) of the cases occur in developing countries. In developed countries, cervical cancer screening programs have reduced the incidence of cervical cancer by 75% due to the detection, follow-up, and treatment of premalignant lesions. Despite this success, ~10,000 cases of cervical cancer still occur annually in the US, causing over 3000 annual deaths [10; 11], and more than 30,000 cases of cervical cancer still occur annually in the European Union, causing over 13,000 annual deaths [12].

**Anogenital Warts.** Anogenital warts are generally benign, exophytic, hyperkeratotic lesions appearing over the vulva, urethra, vagina, perineum, and anus in women, and on the penile shaft (most common site of lesions), scrotum, perineum, and anus in men. In general, the lesions do not cause any physical discomfort [13]. Some patients experience itching, burning, bleeding, moisture, irritation or soreness, especially with lesions in the perianal region. Patients are often distressed by unsightly lesions. Treatment consists of chemical or physical ablation and is often unsuccessful. Recurrence rates are high [14].

**Anal, Vulvar, Vaginal and Penile Cancer.** Most anal cancers, and ~50% of vulvar, vaginal and penile cancers, are caused by HPV. Rates of anal cancer (men and women) and HPV-related vulvar and vaginal cancers are increasing [5; 15].

**Recurrent Respiratory Papillomatosis.** RRP is a rare but severe disease that is manifested as rapidly-growing exophytic warts in the upper airway, most often in the larynx, causing severe respiratory and speech impairment. Repeated surgical excision is often needed. The disease tends to recur despite repeated treatment and can lead to death by blocking the airway. RRP is primarily caused by HPV Types 6 and 11. The disease occurs in both children and young adults [16; 17; 18; 19; 20].

**Other HPV-associated malignancies.** HPV causes  $\sim 25$  to 30% of cancers of the oral cavity, oropharynx, and larynx [21]. When oropharyngeal cancers are considered alone, the percentage caused by HPV is notably higher. HPV may also be associated with cancers involving the aerodigestive tract, including cases of lung and esophageal cancers [22; 23], as well as bladder cancers [24].

### 3.1.1.2 Biology of Human Papillomavirus

HPV consist of a family of small, nonenveloped icosahedral capsid viruses containing double-stranded DNA composed of 8 early transcribed open reading frames, two late open reading frames, and a non-coding long control region [25]. The Late (L) genes encode the 2 capsid proteins (L1, major capsid protein) and L2 (minor capsid protein). Even though present in mature viral particles, L2 proteins are not necessary for capsid formation. Proteins encoded on the early (E) portion of the genome are involved in viral DNA synthesis. E6 and E7 proteins induce epithelial cell hyperproliferation by inhibiting cell cycle regulatory proteins, a likely mechanism by which all HPV types cause aberrant proliferation of infected cells [26; 27].

22

The HPV family of viruses represents nearly 100 related epitheliotropic DNA viruses that have been classified by types and species [28]. HPV types (also referred to as genotypes) are defined based on DNA sequencing [10]. Overall, 40 HPV types can infect the anogenital tract. Although all HPV types appear to disrupt the cell cycle regulator mechanisms, true oncogenic potential is limited to a subset of HPV types. Clinically, HPV types are classified into high-risk (HR) types (cancer-causing: i.e., in descending order of frequency in tumor specimens HPV 16, 18, 45, 31, 33, 52, 58, 35, 59, 56, 39, 51, 73, 66, 68) [10], and low-risk (LR) types (causing generally benign lesions: e.g., HPV 6, 11, 42, 43, 44).

Phylogenetically, HPV are classified into several species. HPV types targeted by prophylactic HPV vaccines belong to Species A7, A9, and A10. Species A7 and A9 contain most of the HR types. The A7 Species includes HPV 18, 39, 45, 59, and 68. The A9 Species includes HPV 16, 31, 33, 35, 52, and 58. HPV 16 and 18 are responsible for most (~70%) cases of cervical cancer, with an additional ~20% due to HPV Types 31, 33, 45, 52, and 58 [8]. The proportion of cervical cancers caused by types other than HPV 16 varies by region. For example, in Western countries, HPV 18 is the second most common cause of cervical cancer. However, in East Asia, HPV 52 and 58 are responsible for a higher proportion of cervical cancers than HPV 18. Species A10 contains LR HPV Types 6 and 11, which are responsible for over 90% of anogenital warts and RRP cases.

HPV infection and replication is entirely intraepithelial. The basal cell of the epithelium is the primary target of HPV infection. A minor lesion in the epithelium is enough to allow HPV to access this layer of cells [29]. Viral replication occurs only at a low level in the basal cells. High-level viral protein expression is achieved in the middle or upper layers of the epithelium. These layers of epithelial cells are normally terminally differentiated. However, with the up-regulation of viral proteins E6 and E7 that takes place during HPV infection, these cells are maintained in a mitotically active state that is conducive to viral DNA and protein synthesis [30]. Viral assembly takes place only in terminally differentiated cells at the epithelium surface. Viral shedding occurs through the routine desquamation of dead epithelial cells [31; 32; 33].

